A total dose of 80 Gy will be delivered in 40 fractions to the Clinical Target Volume (CTV).
- Arm II: Hypofractionated Targeted Intensity Modulated Radiotherapy (HTIMRT)
Dose escalation to the Multiparametric MRI (MP-MRI) by dose painting at 2.35-2.40 Gy per fraction, while the rest of the Clinical Target Volume (CTV) receives 2.0 Gy a fraction to 76 Gy. The hypofractionated targeted (HT) boost region will receive an absolute dose of 89.3-91.2 Gy. Assuming an α/β ratio of 3.0, this would be equivalent to 95.5 Gy in 2.0 Gy fractions.

2. Stratification

- PSA <10 vs. 10 to \leq 100.
- Gleason Score 6-7 vs. 8-10. (Based on original diagnostic biopsy)
- Short Term Androgen Deprivation (STAD) – 4 to 6 months (Y vs. N).

3. Eligibility Screening: Includes Multiparametric Functional MRI of Prostate and Pelvis

- Biopsy confirmed adenocarcinoma of the prostate.
- T1-T3a disease based on digital rectal exam.
 - T1a is permitted if peripheral zone biopsies are positive.

- b. T3a disease based on MRI only is acceptable (no evidence of frank [clear cut] SV involvement or invasion of bladder or rectum).
- C. No evidence of metastasis by any clinical criteria or available radiographic tests.
- D. Gleason score 6-10.
- E. Patients with Gleason score ≥ 8 must be offered long term androgen deprivation therapy (ADT) and refuse such treatment because only 4-6 months (short term ADT) is permitted on this protocol. Gleason score ≥ 8 patients should be recommended to receive 4-6 months (± 2 months) of ADT. When given, the ADT should begin after fiducial marker placement, if applicable; however, is permitted to have been started up two months prior to the signing of consent.
 - a. Gleason 8-10 must have $<40\%$ of the tissue overall involved with Gleason 8-10 in the biopsy specimen.
 - b. Patients with Gleason score ≤ 7 may be treated with 4-6 months of ADT if $\geq 20\%$ of the biopsy tissue is, or $\geq 50\%$ of the cores are, positive for tumor.
- F. PSA ≤ 100 ng/mL within 3 months of enrollment. If PSA was above 100 and dropped to ≤ 100 with antibiotics, this is acceptable for enrollment
- G. If PSA is >15 ng/ml or there is \geq Gleason 8 disease, a bone scan should be obtained ≤ 4 months before enrollment and should be without evidence of metastasis. A questionable bone scan is acceptable if plain x-rays, CT and/or MRI are negative for metastasis.
- H. No previous pelvic radiotherapy.
- I. No previous history of radical/total prostatectomy (suprapubic prostatectomy is acceptable).
- J. No concurrent, active malignancy, other than non-metastatic skin cancer or early stage chronic lymphocytic leukemia (well-differentiated small cell lymphocytic lymphoma). If a prior malignancy is in remission for ≥ 5 years then the patient is eligible.
- K. Identifiable functional MRI (1.5T or 3.0T MRI) tumor lesion or lesions, that total in volume $<33\%$ of the prostate within 3 months prior to enrollment.
- L. Ability to understand and the willingness to sign a written informed consent document
- M. Zubrod performance status <2 . (Karnofsky or ECOG performance status may be used to estimate Zubrod) See Appendix IV
- N. Willingness to fill out quality of life/psychosocial forms.
- O. Age ≥ 35 and ≤ 85 years.
- P. Serum testosterone is within 40% of normal assay limits (e.g., $x=0.4^*\text{lower assay limit}$ and $x=0.4^*\text{upper assay limit} + \text{upper assay limit}$), taken within 4 months of enrollment. Patients whom have been started on ADT prior to signing consent are not required to have a serum testosterone at this level prior to signing consent; but, a serum testosterone prior to fiducial marker placement is recommended.
- Q. Serum LFTs, taken within 3 months of enrollment.
- R. Complete blood counts, taken within 3 months of enrollment.

4. **Prior to Treatment**

- A. Transrectal research prostate biopsies and gold seed fiducial marker placement, if applicable:
 - a. The pre-RT prostate biopsy is optional for the patient, while the fiducial marker placement is not. For the prostate biopsies, up to a maximum of 14 cores will be taken prior to fiducial marker placement. The number of biopsy cores taken would be up to the discretion of the urologist in conjunction with the team, and

does not have to be defined prior to biopsy if the patient agrees to undergo the procedure.

- b. Ultrasound-guidance is standard for prostate biopsies. The Eigen Artemis® system may be used to fine tune the biopsy locations within the prostate using software to fuse the multiparametric MRI to the ultrasound in real time as the ultrasound is acquiring the images. In addition, these biopsies may be obtained on an MRI directly using established techniques.
- c. 3-4 gold seeds placed in prostate (4 preferred)

B. MRI-simulation: Limited study without contrast at least 1 week after gold fiducial placement.

C. CT-simulation and planning.

5. Treatment Technique

Treatment should start within 6 weeks of fiducial marker placement, if applicable.

A. Arm I: SIMRT

The Gross Tumor Volume (GTV) will be defined by the hypervascular region on DCE-MRI, except for anterior lesions, which must also have restricted water motion on DWI and/or increased choline + creatinine relative to citrate (≥ 0.9 ratio). For the SIMRT patients, the dose to the GTV will be the same as that to the CTV. The CTV, at the minimum, will include the prostate (including the GTV) and the proximal seminal vesicles (usually 7-10 mm and/or $\leq 50\%$, whichever is less). The clinical target volume (CTV) may include an extra 1-2 mm beyond the GTV in regions of known bulky disease and/or extracapsular extension as determined by the diagnostic biopsy information and/or MRI. The Planning Target Volume (PTV) will be 3-5 mm around the CTV in all dimensions. For tumors at the base, a margin of 5 mm on the proximal seminal vesicles is recommended. At least 95% of the PTV should receive 80 Gy in 40 fractions, at 2.0 Gy per fraction.

IMRT plans will be evaluated by dose-volume histogram analyses. Less than or equal to 17% and 35% of the rectum plus anus (rectanus) should receive ≥ 65 Gy and ≥ 40 Gy, respectively. Less than or equal to 25% and 50% of the bladder should receive ≥ 65 Gy and ≥ 40 Gy, respectively. At least 95% of the PTV should receive the prescription dose.

B. Arm II: HTIMRT

The dose to the functional MRI-defined dominant region(s) will be escalated by dose painting at 2.35 Gy per fraction. The HT boost region (GTV) will receive an absolute dose of 89.3 Gy. Assuming an α/β ratio of 3.0, this would be equivalent to 95.5 Gy in 2.0 Gy fractions. The GTV region will be shaped such that the posterior edge is ≥ 2 mm from the rectum to avoid excessive dose to the rectum. The maximum point dose to the rectum per day should not exceed 2.25 Gy. The normal tissue constraints are otherwise the same as for Arm I, considered in 2.0 Gy equivalent doses. The CTV volume is the same as for Arm I; at least 95% of the PTV should receive 76 Gy in 38 fractions, at 2.0 Gy per fraction.

HYPOTHESES

1. Delivery of directed hypofractionated targeted (HT) radiotherapy (RT) tumor boost to the dominant tumor lesion in the prostate as identified by multiparametric functional Magnetic Resonance Imaging (MRI).
2. Biomarker expression levels differ in the functional MRI defined suspicious and unsuspicious tumor regions.
3. 10-15% of men undergoing RT have Circulating DNA or tumor cells (CTC) that are related to an adverse treatment outcome.
4. Quality of life will not differ significantly between the treatment arms.
5. Prostate cancer-related anxiety will be reduced in the HTIMRT arm, because the patients will be aware that the dominant tumor will be targeted with higher radiation dose.

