2.2. Secondary Objectives

- To evaluate the impact of an HT boost on acute and late toxicity.
- To evaluate the influence of HTIMRT to health-related quality of life (HRQOL), prostate cancer-specific anxiety and prostate cancer-specific QOL.
- To quantify biomarker expression in different prostate tumor regions, comparing specifically the functional MRI suspicious regions to those that are not suspicious.
- To evaluate the incidence and relationship of circulating free DNA and tumor cells to tissue biomarkers and prostate biopsy positivity at 2 years after completion of therapy.
- To record other biochemical failure, clinical failure and mortality endpoints.

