14.2 Sample size, accrual rate and study duration

Study size is based on our primary objective of demonstrating that, compared to SIMRT, HTIMRT reduces the two year post treatment failure rate, by which we mean the proportion of patients with either biopsy failure or earlier evidence (within two years of treatment completion) of biochemical and/or clinical failure. (See definition in Section 9.1.) We expect the two-year failure rate in the standard fractionation arm to be 52.5%, representing the combined effect of a small rate of biochemical or clinical failure within two years, approximately 5%, and a relatively high rate of positive biopsy among the remaining 95% of patients, namely 50% ($0.05 + 0.95 \times 0.50 = 0.525$). This estimate is based on prior findings on randomized trials previously

organized by the PI. (75) Assuming equal allocation of patients to SIMRT and HTIMRT and sufficient follow-up to determine failure status at two years, a study size of 36 patients in each treatment arm provides 80% power to detect an absolute reduction of 30% in the two-year failure rate (biochemical, clinical, or biopsy), from 52.5% to 22.5%, using a one-sided Fisher's exact test with 5% significance level. To ensure a minimum of 72 study patients evaluable for the two year failure rate as our main study endpoint, we plan to enroll a total of 76 patients.

Based on an accrual rate averaging 2 patients per month, we plan to complete enrollment in 3.2 years. Patients will be followed for five years giving total study duration of 8.2 years. Analyses of some secondary endpoints, including acute toxicity, psychosocial parameters, biomarker distribution on ultrasound-guided biopsies, and initial MRI findings may be reported before the efficacy endpoints, including the primary endpoint. These secondary endpoints will be analyzed after all planned patients have been accrued, completed treatment and have a minimal potential follow-up of 3 months from the end of RT. The main efficacy endpoint requires less than five years follow up and will be performed after all patients have been assessed for two year post treatment failure status (2 yr. biopsy). Final efficacy analysis will be at the conclusion of study when patients have been followed for 5.25 years.

14.3 Definitions and endpoints:

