14.5 Analysis plan

The main analysis of study findings will be done by treatment assignment (intention-to-treat) in all patients who meet evaluable criteria as stated in Section 14.3. We will report any instances of treatment crossover. As noted above, analyses of some secondary endpoints, including acute toxicity, psychosocial parameters, tissue and blood product-related biomarker distribution on ultrasound-guided biopsies, and initial MRI findings may be reported before the efficacy endpoints, including the primary endpoint. These secondary endpoints will be analyzed after all planned patients have been accrued, completed treatment and have a minimal potential follow-up of 3 months from the end of RT. An initial analysis of clinical outcome (efficacy) is

planned after all patients have been assessed for two year post treatment failure status and a final analysis will be done at the completion of the planned 5 year follow up of all study patients. Statistical tests comparing treatment arms will be one-sided with 5% significance level and stratified where appropriate by the factors considered in randomization.

Statistical analysis will include descriptive statistics for patient demographics and baseline disease characteristics, both overall and by treatment arm. Counts and percentages will be used to summarize the distribution of categorical variables while median, range, mean and standard deviation will be used for continuous variables. Baseline characteristics will include age, sex, race/ethnicity, T-category, Gleason score, PSA, risk group and performance status. Biomarker measurements and proteomic/genomic profiles obtained from baseline biopsy will also be summarized with descriptive statistics. (76)

Treatment received will be summarized by the type of RT and STAD components of therapy, the number and duration of treatment delays, and the rates of discontinuation or completion. Summaries will be provided for each treatment arm. Safety analysis will include a detailed tabulation of acute and late occurring toxicity by type and grade, both overall and by treatment arm. Additionally, we will estimate the cumulative incidence (from start of treatment) of grade 2+ and 3+ genitourinary (GU) toxicity and of grade 2+ and 3+ gastrointestinal (GI) toxicity in each treatment arm. Death without the toxicity of interest will be treated as a competing risk, and toxicity rates will be compared by treatment arm using Gray's test. (77, 78)

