Finally, to assess the prognostic value of 2-year post treatment biopsy findings, we will further study patients who had this procedure without prior evidence of biochemical or clinical failure. Taking the date of biopsy as the start of follow up, we will analyze subsequent failure rates and failure-free survival and test for association with biopsy positivity and treatment arm.

QOL scores will be calculated in accordance with established scoring methods for each instrument. Descriptive summaries of scores at baseline and each subsequent follow up will include median and range, means and standard deviations. Where criteria for clinically meaningful differences have been established, we will also categorize changes in these scores (computed by subtracting baseline from subsequent score) as indicating improvement,

worsening, or no change and summarize these by counts and percentages. Comparison by treatment arm at baseline and at treatment completion will be based on t-test (average score) and Fisher's exact test (percent improved). Further analysis allowing for repeated measurement will be conducted using mixed models.

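### The quality-of-life hypothesis is worded as non-significance and the plan gives no margin or interval criterion by which to judge it

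*Combined protocol and SAP*

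**What the plan says.** The Hypotheses list before Section 1.0 gives, as item 4, "Quality of life will not differ significantly between the treatment arms". The matching secondary objective in Section 2.2 is open-ended: "To evaluate the influence of HTIMRT to health-related quality of life (HRQOL), prostate cancer-specific anxiety and prostate cancer-specific QOL".

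For the arm comparison, Section 14.5 says "Comparison by treatment arm at baseline and at treatment completion will be based on t-test (average score) and Fisher's exact test (percent improved"), and then "Further analysis allowing for repeated measurement will be conducted using mixed models". The contrast, covariates and decision rule of those models are not given. The general rule in the same section is that "Statistical tests comparing treatment arms will be one-sided with 5% significance level"; no direction is stated for QOL.

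Meaningful differences enter once, in Section 14.5: "Where criteria for clinically meaningful differences have been established", changes from baseline will be classed as improvement, worsening or no change. No values are given, and the criteria are not applied to the difference between arms.

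The sample size in Section 14.2 rests on the two-year failure rate alone: "a study size of 36 patients in each treatment arm provides 80% power to detect an absolute reduction of 30" percentage points, and "we plan to enroll a total of 76 patients". There is no QOL power figure, SD or margin in the documents.

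**The concern.** A prediction of no significant difference is met by failing to reject, and failing to reject becomes easier as data become fewer or noisier. The planned t-test and Fisher's exact test can show that the arms differ; neither can show that they are alike. A report that follows the hypothesis wording could therefore present dose escalation as free of QOL cost when the trial was only too imprecise to see one.

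Two features add to this. Sections 14.2 and 14.5 allow psychosocial results to be reported before the primary endpoint, so such a statement could stand alone for some time. And if the one-sided rule is applied in the direction of benefit from HTIMRT (the direction of the primary test, and of Hypothesis 5 on anxiety), the test would be almost blind to harm.

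**Working it through.** **Plan's own figure.** One-sided Fisher's exact test, 36 per arm, 52.5% versus 22.5%, 5% level. Summing the binomial probabilities of all tables with p ≤ 0.05 gives power 80.3%, against 80% stated in Section 14.2. The design figure reproduces, but it concerns failure, not QOL.

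**Inputs for the QOL illustration.**
- n = 36 per arm: the evaluable number for the two-year endpoint (Section 14.2).
- n = 38 per arm: all 76 enrolled patients give QOL data.
- n = 30 per arm: an assumed case with missing questionnaires.
- Level 5%: one-sided is the Section 14.5 rule; two-sided is shown for comparison.
- True difference d = 0.5 SD: an assumption.
- Baseline correlation r = 0.5 for the adjusted case: an assumption.

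**Miss rate of the t-test.** Power comes from the non-central t with 2n − 2 degrees of freedom and non-centrality d × √(n/2). At n = 36 this is 0.5 × √18 = 2.12, with critical values 1.667 (one-sided) and 1.994 (two-sided).

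| Case, d = 0.5 SD | Missed, one-sided | Missed, two-sided |
|---|---|---|
| 36 per arm | 32.4% | 44.7% |
| 38 per arm | 30.3% | 42.4% |
| 30 per arm | 39.4% | 52.2% |
| 36 per arm, baseline-adjusted, r = 0.5 | about 22% | about 32% |

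In the adjusted row the residual SD is √(1 − 0.5²) = 0.866, so the difference is 0.5/0.866 = 0.577 residual SDs.

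**Precision.** The unadjusted 95% half-width at 36 per arm is 1.994 × √(2/36) = 1.994 × 0.2357 = 0.47 SD. An observed difference just short of two-sided significance, about 0.47 SD, is therefore compatible with a true difference of up to about 0.47 + 0.47 = 0.94 SD.

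**Direction.** If the one-sided test looks for HTIMRT benefit and QOL is truly 0.5 SD worse, non-centrality is −2.12 and the test rejects in fewer than 1 in 1,000 trials. A rejection there would point the wrong way in any case.

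**What an interval criterion would deliver.** Assume a margin of ±0.5 SD and truly equal arms. The two-sided 95% interval lies wholly inside the margin with probability about 12% per domain at 36 per arm unadjusted, and about 35% adjusted at r = 0.5 (simulation). For a one-directional non-inferiority claim with the same assumed margin and 80% power, 50 per arm would be needed at one-sided 5%, or 63 at one-sided 2.5%.

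**The case against.** A reader might infer that the plan will declare QOL equal whenever a t-test is non-significant. The documents do not support that. Section 14.5 contains no rule for accepting Hypothesis 4, Section 2.2 speaks only of evaluating influence, and Section 14.1 lists QOL simply as a comparison between arms. That objection stands. What remains is that the hypothesis is phrased as non-significance and nothing else in the plan says how to judge it.

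The analysis is also wider than one t-test. Means and SDs are summarised at every visit, individual changes are classed where criteria exist, and mixed models use the repeated measurements. A reader given means and SDs by arm could see the uncertainty. This softens the point but attaches no criterion to any of these results.

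A reader might also infer that a half-SD difference is missed at least one time in three whatever the assumptions. That is too strong. The half-SD is not in the documents, the QOL t-test at treatment completion need not be limited to the 36 per arm evaluable at two years, and baseline adjustment lowers the misses. On the plan's one-sided rule the unadjusted figure is 30% if all 76 patients contribute.

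Finally, QOL is secondary, and the harms of the boost are also assessed directly, through cumulative incidence of GU and GI toxicity (Section 14.5) and the toxicity stopping guidelines (Section 14.6). This stands and limits the weight of the point.

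**Conclusion.** The point holds as a gap between hypothesis and analysis: Hypothesis 4 predicts non-significance, the planned arm comparisons are difference tests or models without a decision rule, and non-significance cannot support the claim. This logic needs no effect-size assumption.

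The size is illustrative. For an assumed true difference of 0.5 SD, the miss rate runs from about 22% (one-sided, adjusted at r = 0.5, 36 per arm) to 45% (two-sided, unadjusted, 36 per arm), and rises further if questionnaires are missing. A one-sided test for HTIMRT benefit would almost never flag a half-SD worsening. The primary conclusion is unaffected. This is a worthwhile wording change, not a design fault.

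**What to change.** Reword Hypothesis 4 as estimation of the arm difference in QOL. In Section 14.5:

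- Report, for each QOL domain, the two-sided 95% confidence interval for the baseline-adjusted arm difference. This also removes the uncertainty over the direction of a one-sided test.
- State in advance the clinically meaningful difference for each domain that has an established one.
- Say 'no meaningful difference' only where the interval lies wholly inside that value; otherwise call the domain inconclusive.
- Report domains without an established value as estimates only.

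This needs SAP wording and a table of values, and no extra patients, visits or questionnaires. The cost is candour about precision: on the figures above, most domains will probably be reported as inconclusive even if the arms are truly equal.

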1.0 BACKGROUND

1.1 Study Disease

In 2009 more than 190,000 men were diagnosed with prostate cancer. Despite advances in diagnosis and treatment, failure rates continue to remain high (over 27,000 deaths). Local persistence of prostate cancer treated with RT is under-appreciated. Prostate cancer has a long natural history and the consequences of local persistence may not be realized for over ten years. There is significant evidence in support of doses of 78 Gy or higher for primary treatment of localized prostate.(1) There is some evidence to support,(2) and we hypothesize, that the regions in the prostate with the greatest tumor burden are the regions that are at highest risk of harboring persistent disease after RT. Multiparameter MRI and, in particular, DCE-MRI is very promising for the *in vivo* 3D localization of the dominant tumor area.(3) Delivery of a directed HT tumor boost to the functional MRI-identified dominant tumor lesion in the prostate is expected to increase the chance of complete tumor eradication from the prostate, which is a strong predictor of tumor control biochemically.

Our biomarker studies have revealed that molecular biomarkers found in pretreatment prostate biopsy material are associated with patient outcome. We have published a number of papers on biomarkers, including Ki-67,(4) p53,(5, 6) MDM2,(7, 8) bcl-2 and bax,(9) p16,(10, 11) cox-2,(12) and PKA(13) in which abnormal expression using immunohistochemistry (IHC) has been associated with worse patient outcome after radiotherapy. In addition, we have studied a number of tissue biomarkers in other prostate cancer patient populations that have proven to be associated with either biochemical failure, distant metastasis or mortality. These include HYAL1,(14, 15) osteopontin,(16) IL-8,(16) Vav3,(17) and GRP78.(18) However, no model incorporating such markers has gained acceptance in the clinic. The proposed studies in this protocol will provide the foundation for biomarker collection in different prostate tumor regions, comparing specifically the functional-MRI suspicious and unsuspicious regions.

Circulating tumor cells (CTC) have been correlated with prostate cancer disease progression.(19-21) CTCs, however, have not been adopted clinically because this is a relatively new concept and the technology for isolating CTCs reliably and preserving characteristics is still in evolution. There are data showing the promise of using the presence of CTCs in men with castrate resistant prostate cancer (CRPC) to follow treatment response,(21) but less on the characteristics of the tumor cells at the molecular level or the role of CTCs in men at earlier stages of the disease.

The presence of elevated levels of free circulating cell-free nucleic acids (fcDNA) in cancer patients has been well documented. Our preliminary results indicate that at a cut point of 180 ng/mL, fcDNA levels can differentiate prostate cancer from benign prostatic conditions such as prostatitis (PTIS) and benign prostatic hyperplasia (BPH) in patients with a PSA \leq 8 ng/ml. DNA based biomarkers have promise as markers for targeted therapies since they are

chemically and biologically stable compared to RNA and protein markers. Studies have established that fcDNA in serum and plasma of cancer patients originates from tumor cells and that DNA methylation patterns in serum/plasma fcDNA closely match that of DNA isolated directly from tumor tissue. Hence fcDNA is a potential non-invasive biomarker for cancer with the advantages of high sensitivity and specificity.

Tissue biomarkers, fcDNA and CTCs have shown promise in predicting patient outcome in addition to standard clinical factors. Developing consequent biomarker and CTC models will contribute significantly to better defining the decision points in the patients with prostate cancer, as well as understanding the underlying mechanisms that predispose to progression, failure of primary therapy and/or the presence of occult metastatic disease.

